$$\text{Total Exposure (days)} = (\text{Date of last recorded visit} - \text{Date of first insertion of a depot in either eye}) + 1$$

Total treatment exposure (days) for each subject exposed to study drug will be summarized with continuous descriptive statistics for each treatment group and for all subjects, using the Safety population. A subject listing of treatment exposure will also be produced.

13. Efficacy Analyses

Primary Analysis

The primary analysis of the primary efficacy outcome will employ a linear model of IOP in the primary study eye of subjects in the FAS. The response variable will be IOP at the given visit (2 Week, 6 Week, and 12 Week) and time point (8AM, 10AM, and 4PM), time point specific baseline IOP will be used as a covariate, and treatment will be the main effect factor. Each time point within each visit will be modeled separately.

IOP refers to the single result from the following procedure. IOP will be assessed by two qualified independent study site personnel at each visit and time point using a Goldmann applanation tonometer affixed to a slit lamp with the subject seated. Two measurements should be performed, and if the IOP is within 1 mm Hg, the average of the first two measurements should be recorded. If the IOP from the first two readings shows a greater than 1 mm Hg difference, a third reading should be taken and the average of all three readings recorded. Averages of readings are calculated within the clinical database.

For the primary analysis, MI methods will use the MCMC approach for any data missing from these visits/time points, after LOCF has been used to impute data for time points after the subject's primary study eye is prescribed IOP-lowering drops. Example MCMC imputation code which will be implemented after LOCF has been applied (SAS® version 9.4) is shown here:

```
PROC MI DATA = indata SEED = 7436892 OUT = outdata NIMPUTE=20;
BY TMPTN;
MCMC INITIAL = EM;
VAR trt baseline WV2 WV4 WV6 WV8 WV10 WV12;
```

RUN;

where

- *indata* is the name of the input dataset;
- *outdata* is the name of the output dataset;
- *nimpute* is the number of imputations;
- *tmpn* is the time point of assessment, 8AM, 10AM, or 4PM;
- *trt* is the name of the treatment group variable in numeric format;
- *baseline* is the average IOP at baseline
- *WV2* is the IOP value for the 2 Week visit;
- *WV4* is the IOP value for the 4 Week visit;
- *WV6* is the IOP value for the 6 Week visit;
- *WV8* is the IOP value for the 8 Week visit;
- *WV10* is the IOP value for the 10 Week visit;
- *WV12* is the IOP value for the 12 Week visit.

Twenty complete data sets for each time point will be generated from the above code. The data will be transposed to have a vertical structure with one record per subject, imputation, visit, and time point. Each complete data set will be used to compute the mean IOP and analyze using the linear model with time point specific baseline IOP used as a covariate, and treatment as the main effect factor. A separate model will be fit for each visit/time point combination. Then, the SAS® procedure MIANALYZE will be used to analyze the results from the 20 complete data sets to generate a combined inference. The following SAS® code will be used:

```

ODS OUTPUT LSMEANS = outdataB;
PROC MIXED DATA = outdataA;
CLASS trt;
MODEL IOP = trt baseline;
BY visitn tmpn _IMPUTATION_;
LSMEANS trt/PDIFF CL;
RUN;

```

where

- *IOP* is the IOP for each visit and time point;
- *visitn* is the visit number variable in numeric format;
- *tmpn* is the time point variable in numeric format;
- *baseline* is the average IOP at baseline, matched by time point;
- *trt* is the name of the treatment group variable in numeric format;
- *outdataA* is the transposed dataset containing the 20 “complete” datasets from the imputation.

```

ODS OUTPUT PARAMETERESTIMATES = outdataC;
PROC MIANALYZE DATA = outdataB;
MODELEFFECTS ESTIMATE;
STDERR STDERR;
BY visitn tmpn;
RUN;

```

where

- *outdataB* is the name of the output dataset that contains the statistical results of the difference between treatment groups from the MIXED procedure that is run on each of the twenty imputation datasets;
- *outdataC* is the name of the output dataset that contains all the information needed for the table.

After imputation the least squares mean differences (OTX-TP minus PV) will be presented along with 2-sided 95% confidence intervals (CIs) around the difference and 2-sided p-values testing the difference equal to 0. Inference will be made on the 2-sided p-value at a 2-sided alpha = 0.05 at each time point and visit. The study will be considered a success if the 2-sided p-value < 0.05 (demonstrating statistical superiority) and the point estimate of the difference is < 0 at all time points over the three visits.

Two-sample t-test p-values and two-sided 95% CI's will also be computed around the difference (OTX-TP minus PV) in IOP between treatment groups at each time point and visit for the primary analysis data (FAS employing MI methods using MCMC approach to impute missing data and using LOCF to impute data for time points after a subject's study eye is prescribed IOP-lowering drops as rescue therapy). The following SAS® code will be used for the t-test:

```

ODS OUTPUT STATISTICS = outdataB;
PROC TTEST DATA = outdataA;
CLASS trt;
VAR IOP;
BY visitn tmpn _Imputation_;
RUN;

```

- *IOP* is the IOP for each visit and time point;
- *visitn* is the visit number variable in numeric format;
- *tmpn* is the time point variable in numeric format;
- *baseline* is the average IOP at baseline, matched by time point;
- *trt* is the name of the treatment group variable in numeric format;
- *outdataA* is the transposed dataset containing the 20 "complete" datasets from the imputation.

Then, as with the PROC MIXED results, the SAS® procedure MIANALYZE will be used to analyze the results from the 20 complete data sets to generate a combined inference.

```
ODS OUTPUT PARAMETERESTIMATES = outdataC;  
PROC MIANALYZE DATA = outdataB;  
MODELEFFECTS ESTIMATE;  
STDERR STDERR;  
BY visitn tmptn;  
RUN;
```

where

- *outdataB* is the name of the output dataset that contains the statistical results of the difference between treatment groups from the MIXED procedure that is run on each of the twenty imputation datasets;
- *outdataC* is the name of the output dataset that contains all the information needed for the table.

Sensitivity analyses for the primary efficacy endpoint include both linear models of IOP and 2-sample t-tests presented on the FAS population using (1) MI approach using MCMC to impute non-monotone missing information and a pattern mixture model control-based pattern imputation for monotone missing information to impute both missing data and data after a subject's primary study eye is prescribed IOP-lowering drops as rescue therapy, (2) using LOCF to impute both missing data and data after a subject's primary study eye is prescribed IOP-lowering drops as rescue therapy, (3) using BOCF to impute both missing data and data after a subject's primary study eye is prescribed IOP-lowering drops as rescue therapy, and these analyses using observed data only (excluding data after a primary study eye is prescribed rescue therapy) for the (4) FAS and (5) per protocol populations.

For multiple imputations using a control-based pattern-mixture model, a process will be used that is similar to multiple imputations using MCMC. Twenty "complete" (imputed) datasets will be produced and analyzed. Results from the analyses on the twenty "complete" datasets will be combined for presentation through the use of SAS® PROC MIANALYZE. Time point specific baseline IOP will be used as a covariate, and treatment will be the main effect factor. A separate model will be fit for each visit/time point combination. Monotone missing information refers to data missing from any visits beyond a subject's final visit (at which IOP is assessed) up to and including the 12 Week Visit. Non-monotone missing information refers to data from missed visits between any two visits at which IOP is assessed. First LOCF will be used to impute data for time points after a subject's primary study eye is prescribed IOP-lowering drops. Then MCMC will be employed to impute any non-monotone missing information using the code:

```
PROC MI DATA = indata SEED = 3335891 OUT = mondata NIMPUTE=1;  
BY TMPTN;
```

```
MCMC INITIAL = EM IMPUTE = MONOTONE;
VAR trt baseline WV2 WV4 WV6 WV8 WV10 WV12;
RUN;
```

where

- *indata* is the name of the input dataset;
- *mondata* is the name of the output dataset;
- *nimpute* is the number of imputations;
- *trt* is the name of the treatment group variable in numeric format;
- *baseline* is the average IOP at baseline;
- *WV2* is the IOP value for the 2 Week visit;
- *WV4* is the IOP value for the 4 Week visit;
- *WV6* is the IOP value for the 6 Week visit;
- *WV8* is the IOP value for the 8 Week visit;
- *WV10* is the IOP value for the 10 Week visit;
- *WV12* is the IOP value for the 12 Week visit.

Then the following SAS® code will be used to produce twenty “complete” datasets for each time point, imputing monotone missing data using a control-based pattern mixture model:

```
PROC MI DATA = mondata SEED = 48670 NIMPUTE = 20 OUT = outdata
MINIMUM = . . 0 MAXIMUM = . . 70 ROUND = . . 0.25;
BY visitn tmpntn;
CLASS trt;
MONOTONE REG(WV2_8 WV4_8 WV6_8 WV8_8 WV10_8 WV12_8 = baseline /
details);
MNAR model(WV2_8 WV4_8 WV6_8 WV8_8 WV10_8 WV12_8/ MODELOBS =
(TREATMENT="2"));
VAR trt baseline WV2_8 WV4_8 WV6_8 WV8_8 WV10_8 WV12_8;
RUN;
```

After obtaining twenty complete datasets, the data from the two MI procedures will be combined and will then be transposed to have a vertical structure with one record per subject, imputation, visit, and time point. SAS® code similar to what is previously described for multiple imputations in the primary analysis will then be employed to run the model on each dataset and combine results across imputations.

In the case that there is no missing data for a given visit and time point, observed data will be analyzed. Analyses on observed data and without MI methods will use the following statistical models:

```
ODS OUTPUT LSMEANS = outdata;
PROC MIXED DATA = indata;
```

```

CLASS trt;
MODEL IOP=trt baseline;
BY visitn tmptn
LSMEANS trt/PDIFF CL;
RUN;
    
```

where

- *IOP* is the IOP for each visit and time point;
- *visitn* is the visit number variable in numeric format;
- *tmptn* is the time point variable in numeric format;
- *baseline* is the average IOP at baseline, matched by time point;
- *trt* is the name of the treatment group variable in numeric format;
- *indata* is the dataset containing only observed data.

and

```

ODS OUTPUT STATISTICS = outdata;
PROC TTEST DATA = indata;
CLASS trt;
VAR IOP;
BY visitn tmptn;
RUN;
    
```

- *IOP* is the IOP for each visit and time point;
- *visitn* is the visit number variable in numeric format;
- *tmptn* is the time point variable in numeric format;
- *baseline* is the average IOP at baseline, matched by time point;
- *trt* is the name of the treatment group variable in numeric format;
- *indata* is the dataset containing only observed data.

Secondary Analysis

Mean change from baseline IOP and mean percent change from baseline IOP will be analyzed similarly to the primary endpoint analysis, including all sensitivity analyses. (If a subject is missing a baseline IOP value, or if Baseline Visit 2: 4PM IOP is measured after insertion, change from baseline and percent change from baseline are not calculated.) As described above, these analyses involve linear models of the response variables on the FAS population using various combinations of imputation methods [(a) MCMC for missing data, LOCF for timepoints after rescue therapy has been initiated; (b) MCMC for non-monotone missing, pattern mixture models for monotone missing; (c) LOCF for both missing and “rescue” time points; and (d) BOCF for both missing and “rescue” time points] as well as inference on observed data confined to the FAS and Per Protocol populations.

Additional Analyses

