4.5.7.9.5. Unscheduled Visits

For Unscheduled Visits, the reason for the visit should be clearly documented on the appropriate CRF, including findings from all evaluations that are completed. The following evaluations must be completed. Ocular assessments are required to be conducted on both eyes.

- Medication and Medical History Update
- Subject ocular comfort assessment
- Assessment of Ocular complaints
- Assessment of BCVA
- Slit Lamp biomicroscopy
- Assessment and grade of ocular hyperemia (at slit lamp)
- Confirmation of intracanalicular depot presence by visual assessment
- Punctum exam
- IOP measurement
- Adverse event assessment

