For Unscheduled Visits, the reason for the visit should be clearly documented on the appropriate eCRF, including findings from all evaluations that are completed.

Data from unscheduled visits up to the 12 Week Visit will be integrated into subject listings and summary tables. All unscheduled data is presented in listings. Tables will incorporate unscheduled data according to the following rules. If unscheduled data is available within window of a scheduled Visit with missing data, the unscheduled data will be used. If scheduled Visit data is not missing, unscheduled data will not be used. If more than one set of unscheduled data falls within a window for an efficacy assessment, the earliest unscheduled visit in that visit window will be used. If more than one set of unscheduled data falls within a window for a safety assessment, the worst case observation will be used. "Within window" is calculated based on Visit name rather than Visit date.

10. Disposition of Subjects

Subject disposition of all enrolled subjects will be presented in terms of the numbers and percentages of subjects who were screened, screened but not randomized, randomized, completed the study, discontinued from the study and/or experienced protocol deviations. Number of subjects exiting the study prior to Week 12, at Week 12, at Week 20 and beyond Week 20 will also be summarized. Subjects who are not discontinued from the study will be considered study completers. Disposition will be summarized by treatment group and for all subjects. Reasons for subject discontinuation at various decision time points will be summarized.

Subjects who are enrolled but determined to be ineligible during the screening assessment, Run-in visits, IOP confirmation visit, or baseline visits prior to randomization will be considered screen failures, will be withdrawn from the study, and will not require additional study follow-up visits but will be entered in the EDC system with the reason for screen failure delineated. The total number of screened subjects with the number and percentage of screen failure subjects will be presented. The reasons for screen failure will be displayed with the percentages calculated using total number of screen failures as the denominator.

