The observed and change from baseline BCVA will be summarized for the primary study eye and secondary study eye using continuous descriptive statistics by visit for each treatment group and for all actively treated subjects. Additionally, discrete summaries of the worst change from baseline will be presented for both the primary study eye and the secondary study eye with the following groupings based on the logMAR scores: 0 or less, >0 to +0.09, +0.10 to +0.19, +0.20 to 0.29, +0.30 or more.

Visual acuity scores will also be presented in data listings. Subjects who lost three or more lines (equivalent to change from baseline of 0.30 logMAR or more) will be presented in an additional listing. This additional listing will also include subjects for whom vision worsened to the extent that the subject's vision is measured by finger count, hand motion or light perception.

Slit Lamp Biomicroscopy Examination

A slit lamp biomicroscopy examination of the eyelid, conjunctiva, iris, cornea, anterior chamber, lens, and vitreous will be performed at each visit (except the Run-in Visits for Stratum B subjects) at the 8AM time point. The results will be graded as normal, abnormal NCS or abnormal CS.

The results will be summarized using counts and percentages for each treatment group and for all actively treated subjects at each visit for each eye (primary study eye and secondary study eye). Percentages will be based on the number of subjects in each treatment group with responses. Shift tables for the slit lamp biomicroscopy parameters will also be provided comparing each follow-up visit to baseline. A subject listing of the slit lamp biomicroscopy parameters will also be produced.

Dilated Fundoscopy Examination

A dilated funduscopy examination of the macula, peripheral retina, and optic nerve will be performed at Screening, and the 12 Week Visit. The results will be graded as normal, abnormal NCS or abnormal CS. The cup to disc (C/D) ratio will also be measured. Explanation/comment should be provided on the case report form for any abnormal findings.

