Table 14.3.3.1	Best Corrected Visual Acuity by Time Point and Eye	Safety Population
Table 14.3.3.2	Change from Baseline Category in Best Corrected Visual Acuity by Time Point and Eye	Safety Population
Table 14.3.4.1	Slit Lamp Biomicroscopy by Visit and Eye	Safety Population
Table 14.3.4.2	Shifts from Baseline in Slit Lamp Biomicroscopy by Visit and Eye	Safety Population
Table 14.3.5.1	Dilated Fundoscopy Examination by Visit and Eye	Safety Population
Table 14.3.5.2	Shifts from Screening to 12 Week Visit in Dilated Fundoscopy Examination by Visit and Eye	Safety Population
Table 14.3.6	Mean Observed and Change from Baseline in IOP by Time Point and Eye	Safety Population
Table 14.3.7.1	Slit Lamp Ocular Hyperemia by Visit and Eye	Safety Population
Table 14.3.7.2	Shifts from Baseline to Each Post-Baseline Visit in Ocular Hyperemia by Visit and Eye	Safety Population
Table 14.3.8	Mean Observed and Change from Baseline in Subject Ocular Comfort Assessment by Visit and Eye	Safety Population

23. Listings

Listing Number	Title	Population
Listing 16.1.7	Randomization Schedule	All Enrolled Subjects
Listing 16.2.1	Subject Disposition	All Enrolled Subjects
Listing 16.2.2.1	Protocol Deviations	All Randomized Subjects
Listing 16.2.2.2	Inclusion, Exclusion, and Procedural Exclusion Criteria	All Enrolled Subjects
Listing 16.2.2.3	Subjects Excluded from the Per Protocol Population	All Randomized Subjects
Listing 16.2.3	Visit Dates	All Randomized Subjects
Listing 16.2.4.1	Demographics	All Randomized Subjects
Listing 16.2.4.2	Baseline Characteristics: Current Diagnosis, Gonioscopy, Punctum Size, Cup to Disc Ratio, and Intraocular Pressure	Full Analysis Set
Listing 16.2.4.3	Pre-Treatment Perimetry	All Randomized Subjects

Listing Number	Title	Population
Listing 16.2.4.4	Pre-Treatment Pachymetry	All Randomized Subjects
Listing 16.2.4.5	Non-Ocular Medical History	Safety Population
Listing 16.2.4.6	Ocular Medical History	Safety Population
Listing 16.2.4.7	Prior and Concomitant Non-Ocular Medications	Safety Population
Listing 16.2.4.8	Prior and Concomitant Ocular Medications	Safety Population
Listing 16.2.4.9	Pregnancy Test Results	Safety Population
Listing 16.2.5.2	Insertion of Intracanalicular Depot	All Randomized Subjects
Listing 16.2.5.3	Investigator Intracanalicular Depot Visualization and Patency Check	Safety Population
Listing 16.2.5.4	Removal of Intracanalicular Depot	Safety Population
Listing 16.2.6.1	Intraocular Pressure	Safety Population

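### Under SAP v2.0 Section 9, a vision loss seen only at an unscheduled visit can be left out of the promised worst-change summary of BCVA

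*SAP*

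**What the plan says.** SAP v2.0, Section 9, Unscheduled Visits, governs how these records enter the output.

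- Scope: "Data from unscheduled visits up to the 12 Week Visit will be integrated into subject listings and summary tables". A second sentence sends every unscheduled record to the listings without a time limit ("All unscheduled data is presented in listings"), so the Week 12 limit affects tables only.
- Substitution: "If unscheduled data is available within window of a scheduled Visit with missing data, the unscheduled data will be used".
- Bar: "If scheduled Visit data is not missing, unscheduled data will not be used".
- Several unscheduled records: "If more than one set of unscheduled data falls within a window for a safety assessment, the worst case observation will be used".
- Windows are assigned by visit name, not by date.

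SAP v2.0, Section 14, Best Corrected Visual Acuity, states that "discrete summaries of the worst change from baseline will be presented" for each eye, in logMAR categories of which the top one is +0.30 or more. Section 22 lists Table 14.3.3.2 as "Change from Baseline Category in Best Corrected Visual Acuity by Time Point and Eye". No table in that list is titled as worst change.

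Protocol 4.5.7.9.5 says of unscheduled visits: "The following evaluations must be completed". Its list includes BCVA, slit lamp, hyperaemia grade, punctum examination, comfort and IOP, so the data will exist.

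**The concern.** Unscheduled visits can be driven by symptoms: the discharge instructions (Protocol 4.5.7.6.3) tell subjects to call about excessive pain, loss of vision or increasing redness. A worst-change summary is the one planned tabulation of measured vision meant to catch a subject's largest loss. The Section 9 rule can work against it. The same bad reading counts if the scheduled examination was missed, and is dropped if the scheduled examination was done and was better.

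At stake is the count by arm of subjects losing three lines or more. A smaller gap concerns time after Week 12. Depots replaced from Week 6 onwards stay in place until Week 20, but an unscheduled examination after Week 12 enters no visit-based table.

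**Working it through.** The plan gives no expected number of unscheduled visits and no expected rate of vision loss, so there is no figure to reproduce. The check applies the rule as written.

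**Step 1. What the rule returns for one eye and one visit window, up to Week 12.**

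| Scheduled value | Unscheduled values in the window | Value in a safety table |
|---|---|---|
| present | any | scheduled value |
| missing | one | that value |
| missing | several | the worst of them |

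The worst-case sentence operates only in the last row. It never sets an unscheduled value against a scheduled one.

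**Step 2. Example subject.** The values are illustrative changes from a baseline of 0.00 logMAR.

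- Scheduled: Week 2, 0.00; Week 4, +0.04; Week 6, +0.02; Week 8, +0.02; Week 10, 0.00; Week 12, +0.02; Week 20, +0.04.
- Unscheduled, in the Week 4 window: +0.34.

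At 0.02 logMAR per letter (Protocol Appendix B), 0.34 / 0.02 = 17 letters, which exceeds the 15-letter, three-line threshold. 0.04 / 0.02 = 2 letters.

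- Worst change from the records the rule admits: +0.04, in the category above 0 and up to +0.09.
- Worst change from all records: +0.34, in the category of +0.30 or more.

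Now let the Week 4 scheduled value be missing, with two unscheduled values of +0.10 and +0.34. The rule returns +0.34. The recorded worst loss thus depends on whether a milder scheduled reading exists.

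**Step 3. Direction.** A maximum over a subset of records cannot exceed the maximum over all of them. The summary can be equal to or below the true worst change, never above it.

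**Step 4. Text against table list.** Section 14 describes one worst change per eye. The title of Table 14.3.3.2 describes one category per time point. If the table is by time point, it is right for each scheduled visit, but the promised summary is absent. If it is worst change, it is present but can be too low. Protocol 6.13 plans acuity summaries by time point; SAP Section 1 says its own methods supersede the protocol's, so the SAP has to say which is meant.

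**Step 5. Illustrative size. Both rates are assumptions.** Let u be the share of subjects with an unscheduled visit in a window that also has scheduled data, taken as 5% to 20%. Let q be the share of those whose loss of 0.30 or more appears only there, taken as 5% to 25%. The share missed from the top category is u × q.

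| u | q | u × q | of 330 (OTX-TP) | of 220 (PV) |
|---|---|---|---|---|
| 5% | 5% | 0.25% | 0.8 | 0.6 |
| 10% | 10% | 1% | 3.3 | 2.2 |
| 20% | 25% | 5% | 16.5 | 11.0 |

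The same rates are used in both arms, so the table says nothing about a difference between them.

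**The case against.** The strongest reply is that adverse events are the main safety analysis (Protocol 6.13) and are outside this rule. Treatment-emergent events are defined by onset or worsening after insertion, are reported until study exit, and are tabulated by arm. SAP v2.0 adds a special-interest table that includes conjunctival and ocular hyperaemia and iritis. A 17-letter loss meets the anticipated event of a three-line worsening in Protocol 5.5.1. Subjects losing three lines or more also have their own listing, and listings carry the treatment received, so nothing is hidden.

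Most of this stands, but the backstop is partial. Hyperaemia is an adverse event only if the subject complains of it or is discontinued for it. Protocol 5.5 asks sites to record the diagnosis rather than the symptom, and uses vision loss as an example of a symptom, so a measured loss may be coded under another term. A listing gives no planned rate by arm.

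Four stronger readings are tempting, and the documents do not support them:

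- *A reader might infer that safety tables in general ignore unscheduled findings.* The event tables do not. The trigger is also missing data, not attendance: an attended visit with a missed assessment can still be filled.
- *A reader might infer that the hyperaemia and slit-lamp shifts are understated.* They are planned visit by visit, and the scheduled examination is the right value for its row. They do not show transient findings, but no worst-shift summary is promised.
- *A reader might infer that follow-up of retained or replaced depots goes untabulated.* The 20 Week Visit is scheduled and unaffected. The returns every 30 days after it are required by the protocol, and no text classes them as unscheduled; their handling is simply unstated.
- *A reader might infer a bias between arms towards no harm, or multiply an assumed visit rate by 550 (5% to 15% gives about 28 to 83) and call the result missed harm.* The first needs a difference between arms that the documents do not give. The second counts people with an extra visit, not people whose worst value is lost.

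**Conclusion.** The point holds in a limited form. As written, Section 9 can give too low a value for a safety summary that Section 14 promises, and the table list no longer matches that promise. The direction is certain: the worst change in BCVA can be understated and cannot be overstated. The size is unknown. Under the assumed rates above, 0.25% to 5% of subjects would be missed from the top category, and that range rests on the assumptions alone. The conclusion depends on reading the bar on unscheduled data as covering the worst-change summary, which is the plain reading, because the rule is stated for tables without exception. By-visit tables are correct for what they show. The plan should be changed, but this is not evidence that the safety comparison as a whole is biased.

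**What to change.** In SAP Section 9, limit the bar on unscheduled data to by-visit rows. Add one sentence stating that the worst-change summary of BCVA uses every assessment after insertion, scheduled or unscheduled, through study exit, and say whether the returns after Week 20 are included. Then make the title and content of Table 14.3.3.2 agree with Section 14. State how an unscheduled record is assigned to a window, since a visit-name rule alone leaves that open.

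Optionally, add a worst post-baseline row by arm for hyperaemia grade and slit lamp. This would be an addition, not the repair of a promised output.

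The cost is one sentence, one table alignment and some programming on data already required. There are two downsides. Safety figures may become slightly less favourable. A worst value also rises with the number of examinations, so an arm seen more often has more chances to record a bad one. Show the number of unscheduled visits by arm beside the summary so that readers can allow for this.

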Intracanalicular Depot Insertion																									
Intracanalicular Depot Presence														X						X					X
Assessment of Ocular Complaints														X						X					X
Adverse Events	X							X		X				X						X					X
Record Medications	X							X		X				X						X					X

5. Study Treatments

There are two study treatments, OTX-TP intracanalicular depot and PV intracanalicular depot, which are explained below.

OTX-TP Intracanalicular Depot

The OTX-TP drug product is a fluorescent dried polyethylene glycol based, rod-shaped hydrogel intracanalicular depot designed to be placed in the superior or inferior canaliculus. The hydrogel swells on contact with moisture to occlude the lumen, thus holding the OTX-PV in place. Once OTX-TP swells to fill the canaliculus, it is contained in the canaliculus until the hydrogel is resorbed. OTX-TP contains conjugated fluorescein to serve as a visualization aid through the use of a blue light source and yellow filter to confirm product presence.

Placebo Vehicle Intracanalicular Depot

The PV consists of the same components as OTX-TP, except that it does not contain travoprost. The PV will be provided in the same packaging as OTX-TP to maintain masking for the clinical trial.

Method of Assigning Subjects to Treatment Groups

Prior to the initiation of the study, a treatment randomization scheme will be generated using a 3:2 ratio (Active Treatment to Placebo Control) approximately 330 subjects in the OTX-TP arm and 220 in the PV arm. The study will be supplemented with additional subjects for whom bilateral depot insertion is successful in order to ensure that at least 490 subjects who receive a depot bilaterally are followed through the 12 Week Visit for safety and efficacy.

Once it is determined that the subject continues to meet eligibility for the study at Baseline Visit 2, the subject will be randomized into the study through assigning the next sequential kit within the kits corresponding to the subject's previous ocular anti-hypertensive therapy category. Both eyes will be provided with the same assigned treatment, OTX-TP or PV. Randomization will be stratified by investigational site (i.e., one randomization schema per study site) and previous ocular anti-hypertensive therapy with three stratum levels below:

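### Randomisation is stratified by site and prior-therapy stratum, but the analysis and imputation models contain neither; adding stratum is nearly free, for a gain that is small and may be zero.

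*SAP*

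**What the plan says.** SAP v2.0, section 5 (Method of Assigning Subjects to Treatment Groups), and protocol section 4.5.5 define the allocation: "Randomization will be stratified by investigational site (i.e., one randomization schema per study site) and previous ocular anti-hypertensive" therapy, the latter in three levels. Stratum A came in on a prostaglandin, B was treatment-naïve, and C had recently left another ophthalmic study.

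SAP v2.0, section 13 (Primary Analysis), fits each of the nine visit-by-time-point models with two terms: "time point specific baseline IOP will be used as a covariate, and treatment will be the main effect factor". The code agrees: "MODEL IOP = trt baseline". Protocol section 6.11 specifies the same model, so this is a planned choice and not a coding slip.

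The remaining steps follow the same pattern:
- Primary imputation, and the first step of the control-based analysis: "VAR trt baseline WV2 WV4 WV6 WV8 WV10 WV12".
- Control-based analysis model: "Time point specific baseline IOP will be used as a covariate, and treatment will be the main effect factor".
- Control-based imputation, where baseline is the only predictor named: "MONOTONE REG(WV2_8 WV4_8 WV6_8 WV8_8 WV10_8 WV12_8 = baseline".
- Analyses without multiple imputation: "MODEL IOP=trt baseline".

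Stratum is used analytically only in section 13.1.1, where the primary strategy is repeated separately within each stratum. Section 19, which lists departures from the protocol, does not discuss the omission.

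**The concern.** The protocol revision history records that the strata were added to randomisation to balance the arms on recent IOP-lowering therapy, so the sponsor thought the factor might matter for IOP. Stratifying the allocation removes most of the between-arm difference that stratum could cause. A model without stratum still counts the variation between strata as residual error. To the extent that stratum predicts IOP after baseline adjustment, the estimated standard error is larger than the true one and each test is slightly conservative.

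Success requires all nine tests to be significant, so a small loss of precision at each test accumulates. Fitting the strata separately does not recover the loss, because it does not reduce the residual variance in the pooled primary test.

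**Working it through.** **Inputs from the documents** (SAP v2.0, section 6; protocol 6.7): SD 3.75 mmHg, difference 1.5 mmHg at every time point, 294 versus 196 subjects, two-sided alpha 0.05, nine tests that must all succeed, independent time points.

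**Input not in the documents:** R², the share of residual variance that stratum explains after treatment and baseline. It is assumed at 0, 1, 2, 5 and 10%.

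**Step 1: the plan's own figure.**
- k = √(1/294 + 1/196) = 0.0922, so SE = 3.75 × 0.0922 = 0.3458.
- Noncentrality = 1.5 / 0.3458 = 4.338. Single-test power (noncentral t) = 0.9911.
- All nine: 0.9911⁹ = 92.3%. The stated power above 90% reproduces.

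**Step 2: power with and without stratum, under the same stratified design.** With ideal balance on stratum, the estimate has standard deviation 3.75 × √(1 − R²) × k in both analyses.
- Adjusted: noncentral t with that SD. Residual degrees of freedom fall from 487 to 485.
- Unadjusted: the same estimate is tested against an SE that still contains the R² share, integrating over the chi-square distribution of the residual variance.
- Excess CI width without adjustment = 1/√(1 − R²) − 1.
- Stratum gap needed to produce R², for an assumed 60/40 split (A versus B and C together) = √R² × 3.75 / √(0.6 × 0.4).

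| Assumed R² | Excess CI width | Type I error per test, unadjusted | All-nine power, unadjusted → adjusted | Same, correlation 0.5 | Gap needed (mmHg) |
|---|---|---|---|---|---|
| 1% | 0.5% | 4.89% | 92.50 → 92.69% | 94.66 → 94.79% | 0.77 |
| 2% | 1.0% | 4.77% | 92.73 → 93.10% | 94.81 → 95.06% | 1.08 |
| 5% | 2.6% | 4.44% | 93.42 → 94.27% | 95.27 → 95.83% | 1.71 |
| 10% | 5.4% | 3.89% | 94.50 → 95.92% | 95.99 → 96.95% | 2.42 |

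At R² = 0, adding stratum costs less than 0.01 point of power. The correlation column assumes an exchangeable correlation among the nine time points and uses a normal approximation. With an assumed 80/20 split the gaps are larger: 0.94, 1.33, 2.10 and 2.96 mmHg. The 5% and 10% rows are outer bounds, because they need a gap between strata larger than the 1.5 mmHg treatment effect the trial is planned on.

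**Step 3: check without ideal balance.** This was a simulation of 20,000 runs per R², with 490 subjects, 50 sites, assumed blocks of 5 within site-by-stratum cells and an assumed 60/30/10 mix of strata. Mean SE, unadjusted / adjusted for stratum: R² 0, 0.3461/0.3465; 1%, 0.3460/0.3447; 2%, 0.3461/0.3430; 5%, 0.3460/0.3376; 10%, 0.3462/0.3287. The pattern is the same.

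**Step 4: site.** In a separate simulation with no true site effect, adding fixed site effects along with stratum raised the mean SE from 0.346 to 0.353. Near-free therefore describes stratum, not 50 fixed site effects.

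**The case against.** A prespecified linear model with baseline as covariate, the same in protocol and SAP, is legitimate, and the omission errs on the conservative side. R² may well be near zero. All strata meet the same baseline IOP limits (protocol 4.4.1). Each is also screened on a 5 mmHg prostaglandin-related change in IOP and has a six-week washout or recovery before baseline (protocol 4.4.1 and Appendix A). After that, little difference between strata need remain. All of this stands, and it is why the gain is described as possibly zero.

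Balance is also imperfect: 50 sites by 3 strata gives about 150 cells for 550 subjects, under 4 per cell. This is true, but incomplete balance moves the unadjusted type I error towards 5% and makes the gain from adjustment slightly larger, so the conclusion does not change.

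Site variation would remain in the residual after the proposed change. That also stands; it is accepted because fixed site effects cost precision when site has no effect.

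Finally, changing the primary model in a late SAP revision is a further departure from the protocol and must be recorded. That is a small administrative cost and no argument against the change while treatment codes remain masked.

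**Conclusion.** The point holds as a minor efficiency improvement that should be made. Neither stratification factor is in the primary, model-based sensitivity or imputation models, and no reason is stated. Nothing in the trial's validity depends on it: type I error is at or below 5%, and the planned power is met without adjustment.

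The plausible gain under the planning assumptions is 0 to 0.4 points of all-nine power (R² 0 to 2%, independent time points), or about 0.1 to 0.2 points at R² of 1% and 2% with correlation 0.5. It is larger if the true effect falls short of plan. At an assumed 1.2 mmHg and independence, adjustment raises all-nine power from 54.9 to 56.2% at R² 2%. Confidence in the size is medium, because R² and the stratum shares are assumptions.

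**What to change.** Before unmasking:

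1. In the nine primary models and the model-based sensitivity analyses, add randomised stratum (A/B/C) as a fixed factor: `CLASS trt stratum; MODEL IOP = trt stratum baseline;`. Leave the two-sample t-tests as they are.
2. In both PROC MI steps that use MCMC, add two 0/1 stratum indicators (sB, sC) to the VAR list after baseline.
3. In the control-based step, add sB and sC to VAR after baseline and to the predictor list (`= baseline sB sC`). Then realign the limits now written "MINIMUM = . . 0 MAXIMUM = . . 70 ROUND = . . 0.25". These appear to follow VAR order, so two further placeholders are needed: `MINIMUM = . . . . 0`, `MAXIMUM = . . . . 70`, `ROUND = . . . . 0.25`.
4. Record the change in SAP section 19. If stratum is left out on purpose, give the reason instead.

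A sensitivity analysis with a random site intercept is optional.

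The cost is SAP wording, one model term (2 degrees of freedom), two indicators in three PROC MI steps, and the predictor list and limits in the third. No new data are needed, since the stratum letter is part of the randomisation number (SAP section 5).
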